Primary Objective:

- To confirm non-inferiority of the OHSU MPC exercise-enabled closed-loop system with missed mealtime insulin detection algorithm as measured by percent of time 70-180 mg/dL on Dexcom G6 CGM as compared to use of the participant's personal closed loop delivery system.

Secondary Objective:

- To confirm non-inferiority of the OHSU MPC exercise-enabled closed-loop system with missed mealtime insulin detection algorithm as measured by other glucose metrics as compared to use of the participant's personal closed loop delivery system.

Study Hypothesis:

We propose that the use of the OHSU MPC exercise-enabled closed-loop system with missed mealtime insulin detection algorithm will be non-inferior within a time in range margin of 7% as compared to the participant's closed loop delivery system in patients with elevated baseline A1C values.

Endpoints

Primary Endpoint:

- Percent of time with sensed glucose between 70-180 mg/dl across the study duration

Secondary Endpoints:

- Percent of time with sensed glucose between <70 mg/dl across the study duration
- Percent of time with sensed glucose <54 mg/dl across the study duration
- Percent of time with sensed glucose >180 mg/dl across the study duration
- Mean sensed glucose across the study duration
- Coefficient of variation of glucose across the study duration
- Mean amount of insulin delivered per day (in units/kg) across the study duration

Study Type

This is a multi-center, randomized, two treatment, crossover non-inferiority trial designed to compare the glucose control resulting from the use of the OHSU MPC exercise-enabled AP system with missed mealtime insulin detection algorithm (Intervention Period) as compared to usual care using a closed loop insulin delivery system, either the t:slim X2 pump with Control IQ or Omnipod 5 system (Control Period).

Study Population

Study population will be participants with type 1 diabetes, ages 18 years of age and older. Up to 36 participants will be recruited to participate in studies across two sites.

Power Analysis

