A sample of 28 subjects provides at least 80% power for testing our primary endpoint in a non-inferiority framework comparing the exercise-enabled MPC algorithm with missed meal insulin detection to use of participant's personal closed loop system. Assumptions informing this calculation were derived from simulations showing an expected mean percent time in range (70-180 mg/dL) for control IQ that was 3.7% lower (as a difference rather than a ratio) and standard deviations (SDs) for the two conditions of approximately 16 to 19. From this, we assume the SD of the within-subject difference will be approximately 17% and use a one-sided paired t test at the 0.025 level of significance for a mean difference of 3.7% time in range versus 6% as the non-inferiority margin. We plan to recruit up to 36 subjects with goal enrollment of 30 subjects (about 15 at each center).

Protocol Summary:

Participants will undergo one 7-day Intervention Period and one 7-day Control Period in randomized order. During the 7-day intervention study, participants will wear an Omnipod to deliver Fiasp insulin and a Dexcom G6 CGM. The CGM system will provide sensed glucose data every 5 minutes. Sensed glucose data will be wirelessly transmitted via Bluetooth Low Energy (BTLE) from the Dexcom G6 transmitter to the smartphone master controller every five minutes. The smartphone will wirelessly communicate via BTLE to an Omnipod through a Personal Diabetes Manager (Insulet Corp.). The closed-loop system will receive activity data through a Polar M600 watch worn by the participant. Participants will eat one meal in clinic and complete system training on Day 1 and then spend the rest of the 7 days at home. During the 7-day Control Period, the participant will continue their usual diabetes care regimen using a t:slim X2 pump with Control IQ enabled or the Omnipod 5 closed loop system.

Participant Criteria

Inclusion Criteria:

1. Diagnosis of type 1 diabetes mellitus for at least 1 year.
2. Age 18 years and older.
3. Current use of a t:slim X2 insulin pump with the use of Control IQ or the Omnipod 5 system with closed loop enabled with Dexcom G6 or G7 for at least 12 weeks.
4. Willingness to use Fiasp insulin during intervention study
5. Lives with another person age 18 or older who will sleep in the house at night and that can attend the training on using the system.

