The primary study endpoint is percent of time in range defined as glucose measured by Dexcom G6 or G7 in the range of 70-180 mg/dL. The hypothesis to be tested is if the MPC exercise-enabled closed-loop system with missed mealtime insulin algorithm will be non-inferior as compared to the participant's personal closed loop system. As our main approach, we will perform a two-sided Wilcoxon test for the paired differences. This test is widely used and easily interpreted. However, it cannot accommodate missing data or estimate crossover effects, and while we do not anticipate that these will affect our study outcomes, we plan to conduct a supplemental analysis using a linear regression model with bootstrapped standard errors, which do not require distributional assumptions. In resampling for the bootstrap, we will use study subjects as the sampling unit to account for correlation between their repeated observations. The general model is as follows:

$$(1) \quad Y_{ij} = \beta_0 + \beta_1 Trt_j + \beta_2 Seq_i + \beta_3 Period_j$$

In this model, the outcome Y_{ij} is the percent of time with sensed glucose 70-180 mg/dL for person i in observation period j . Trt_j represents the treatment arm (MPC=1, Control IQ=0). Seq_i is an indicator for sequence (AB vs BA) and $Period_j$ indicates when Trt_j occurred in the sequence. The coefficient β_0 represents the mean response for Control IQ, and the coefficient β_1 represents the difference between treatments to be tested. The coefficients β_2 and β_3 , mean differences for sequence or period, are both expected to equal zero; a large effect or significance test with p-value <0.05 will be considered evidence of a carryover effect. Hypothesis tests will be two-sided with type I error set to 0.05. Because statistical tests are specified and prioritized *a priori* and our proposed endpoints are highly related, we will follow recommendations to report p-values and confidence intervals rather than adjust for multiple comparisons.

Model fit and alternatives: Goodness of fit statistics and model fitting diagnostics will be used to assess for influential points and to evaluate alternative model specifications. If needed to compensate for some skew and heteroscedasticity in secondary outcomes, we will use bootstrapped variance estimators and compare these against robust estimates.

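### The main test for a non-inferiority hypothesis carries no margin; as written it asks whether the difference is zero, and the stated power does not belong to it

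*Protocol*

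**What the plan says.** The Study Type paragraph opens: "This is a multi-center, randomized, two treatment, crossover non-inferiority trial". The Power Analysis section plans to "use a one-sided paired t test at the 0.025 level of significance"; the margin it tests against is 6%. It takes an SD of 17 for the within-subject difference, an expected advantage of 3.7 points for the new system, and claims at least 80% power with 28 participants. The Study Hypothesis paragraph gives the margin as 7%, not 6%.

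The Statistical methods section begins in the same spirit: "The hypothesis to be tested is if the MPC exercise-enabled closed-loop system with missed mealtime insulin algorithm will be non-inferior". The analysis it then fixes is: "As our main approach, we will perform a two-sided Wilcoxon test for the paired differences". It adds a supplemental regression in which β1 "represents the difference between treatments to be tested", and the general rule "Hypothesis tests will be two-sided with type I error set to 0.05". On reporting, the plan is to "report p-values and confidence intervals rather than adjust for multiple comparisons". No margin appears anywhere in that section, and nothing says which confidence limit will be compared with what.

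**The concern.** A non-inferiority claim needs a null hypothesis of the form: difference (new minus control) at or below minus the margin. A Wilcoxon test on paired differences with no stated shift has a different null, symmetry about zero. The stated hypothesis and the stated test therefore do not match.

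Two things are at stake. First, the power quoted for the trial belongs to another null, so the Protocol does not describe what its main test can be expected to deliver. Second, the most likely outcome of the test as written is a non-significant result, and the Protocol does not say what follows from it. Such a result is no evidence of non-inferiority, yet in a trial that carries that label it could easily be presented as if it were. The margin cannot simply be carried over from elsewhere in the Protocol either, because two values are given.

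**Working it through.** **Inputs.** From Power Analysis: n = 28, SD of the paired difference 17, true difference +3.7 (new minus control), margin 6, one-sided α 0.025. From Study Hypothesis: margin 7. From Statistical methods: two-sided Wilcoxon, α 0.05, no margin. The standard error of the mean difference is 17/√28 = 3.21.

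**Step 1: reproduce the plan's figure.** For the one-sided paired t test at margin 6, the noncentrality is (6 + 3.7)/3.21 = 3.02 on 27 df. Power is 82.9%, and 27 participants are the fewest that reach 80%. The claim of at least 80% with 28 is therefore correct for that test. At margin 7 the noncentrality is 10.7/3.21 = 3.33 and power is 89.4%.

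**Step 2: the test as written, null at zero.** The exact signed-rank critical values for n = 28 are W ≤ 116 or W ≥ 290 (0.0239 in each tail). In 40,000 simulated trials with normal differences, SD 17 and true difference +3.7:
- significant in favour of the new system: 18.5%;
- significant against it: 0.1%;
- not significant: 81.4%.

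As a cross-check, the two-sided paired t test of zero has noncentrality 3.7/3.21 = 1.15 and rejects in favour of the new system in 19.8% of trials. It would need 168 participants for 80%.

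**Step 3: what a non-significant result would be worth.** Same test and simulation, with the new system truly worse:

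| True difference | Not significant |
|---|---|
| −6 | 59% |
| −7 | 47% |

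These would be the false-claim rates if non-significance were taken as non-inferiority. The intended rate is 2.5%.

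**Step 4: the same Wilcoxon test with the margin put in.** Apply it to (difference + margin) and use the upper tail only:

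| Margin | Power at +3.7 | Error rate when the true difference equals −margin |
|---|---|---|
| 6 | 81% | 2.5% |
| 7 | 88% | 2.2% |

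The planned power is recovered with either margin at n = 28.

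**The case against.** The strongest reply is that the Protocol never says the null is zero. The sentence just before the Wilcoxon test names non-inferiority as the hypothesis, a signed-rank test can be centred at any value, and margins do appear elsewhere. Confidence intervals are also promised, and comparing the lower limit of a two-sided 95% interval with minus the margin is a valid non-inferiority test. A statistical analysis plan may exist that says all this.

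Part of this stands. The zero null is what the wording yields by default, not a phrase in the text. But the Protocol names its main test and gives it no shift, and it contains no sentence linking an interval to a margin. A later plan would have to change this test, not just add detail, and would have to choose between 7% and 6%.

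A reader might also infer several stronger things that the document does not support:
- *That the test can never establish non-inferiority.* A significant result in favour of the new system would imply it. That outcome is simply uncommon (about 18.5%) under the planning assumptions.
- *That the plan treats p > 0.05 as non-inferiority.* It nowhere says so. The 59% and 47% are conditional on that misreading.
- *That β1 is tested against zero.* The text says only that it is the difference to be tested. The expectation of zero is stated for the sequence and period coefficients.
- *That two-sided 0.05 conflicts with one-sided 0.025, or that powering on a t test and analysing by Wilcoxon is a fault.* For a non-inferiority decision the two error levels give the same criterion, and the switch of test costs about two percentage points of power (82.9% to 81%).

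**Conclusion.** The point holds: the primary analysis as written does not test the hypothesis the trial was designed for, because the margin is absent from it. The fault is the missing margin and decision rule, not the rank test, its sidedness or the sample size. Under the plan's assumptions, the stated test has about 18.5% probability of a result favouring the new system, against 82.9% for the test that was powered.

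The figures rest on normally distributed differences, an SD of 17, a true difference of +3.7 and 28 complete pairs. The mismatch between hypothesis and test depends on none of these. The statement that the sample size stands does depend on them: at margin 6 the paired t test falls to 78.5% if the SD is 18. This should be corrected before outcome data are seen, since the trial's main conclusion turns on it.

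**What to change.** In the Protocol:

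1. Reconcile the 7% in Study Hypothesis with the 6% in Power Analysis into one prespecified margin.
2. In Statistical methods, state H0: time in range (MPC − control) ≤ −margin.
3. Keep the Wilcoxon test, but apply it to (difference + margin) at one-sided 0.025. Equivalently, declare non-inferiority only if the lower limit of the two-sided 95% Hodges-Lehmann interval lies above −margin.
4. Apply the same confidence-limit rule to β1 in the supplemental model.
5. Test against zero (superiority) only after non-inferiority has been shown.
6. Name the same test in Power Analysis, with about 81% power (margin 6) or 88% (margin 7) at n = 28.

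The cost is a few sentences. No additional participants or data are needed.

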17. Chronic usage of any immunosuppressive medication (such as cyclosporine, azathioprine, sirolimus, or tacrolimus).
18. Bleeding disorder, treatment with warfarin, or platelet count below 50,000.
19. Allergy to Fiasp insulin.
20. Current administration of oral or parenteral corticosteroids.
21. Any life-threatening disease, including malignant neoplasms and medical history of malignant neoplasms within the past 5 years prior to screening (except basal and squamous cell skin cancer).
22. Current use of beta blockers or non-dihydropyridine calcium channel blockers.
23. Current use of any medication intended to lower glucose other than insulin (ex. use of metformin or liraglutide) or SGLT-2 inhibitors (for diabetes or other indications, ex. use of empagliflozin or ertugliflozin).
24. Gastroparesis
25. Low carbohydrate diet at the time of screening defined as less than 50 grams of carbohydrate per day.
26. Any clinically significant disease or disorder which in the opinion of the Investigator may jeopardize the participant's safety or compliance with the protocol.

Participant Recruiting:

Participants will be recruited from 2 sites in the United States, one of which will be Oregon Health & Science University (OHSU). Non-English speaking participants will not be recruited since this protocol would require the use of medical devices and mobile software that do not

have non-English versions available. Up to 60 participants may be screened in this study. Goal enrollment is 30 participants across both sites with up to 6 replacements as needed to collect data from 28 participants. However, re-screening is allowed up to one time per individual, no sooner than 2 weeks and no longer than 3 months and after initial screen. It is anticipated that each site will enroll about 15 participants, but this may be adjusted if needed to complete enrollment in a timely fashion.

Withdrawal Criteria

The participant may withdraw at will at any time or at the discretion of the Investigator.

A participant must be withdrawn if the following applies:

- Severe Hypoglycemia during the treatment period (control or intervention period). Severe hypoglycemia is defined as any event that required the assistance of another person to administer carbohydrate, glucagon, or other resuscitative actions.

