breast and pelvic exams. Females of child-bearing potential will take a urine pregnancy test, which must be negative to participate. A venous blood sample will be taken for the following tests: hemoglobin A1C, complete blood count, and complete metabolic set (including creatinine, liver set, and electrolytes). A study investigator will assess inclusion/exclusion criteria and review the participant's medical record for clarification as needed. When feasible, the participant's insulin pump and glucose sensor, if applicable, will be downloaded before enrollment to obtain the prior 4 weeks of data. A three-digit participant ID number will be assigned to the participant. This visit will take approximately 1.5 hours.

The treatment order will be randomized. The two periods, which are the 7-Day Control Period and 7-Day Intervention Period, will be a minimum of 7 days and a maximum of 8 weeks apart counting from the first day of the first period to the first day of the second period.

A complete list of times when participants will be instructed to take SMBG readings is listed below.

Participants will be instructed to take SMBG readings under the following conditions:

1. If the sensor glucose is $<70\text{mg/dL}$, the system will prompt a SMBG be entered. (intervention period only)
2. If the sensor glucose is $\geq 300\text{ mg/dl}$ for 30 minutes within the last 45 minute period, the system will prompt a SMBG be entered. (intervention period only)
3. If participant's symptoms (such as symptoms of hypoglycemia or hyperglycemia) are discrepant with the Dexcom CGM reading, then the participants will be instructed to perform a SMBG and use this value to make treatment decisions and to calibrate the Dexcom device. (Intervention and control period)
4. If CGM value is unavailable, a SMBG will be required to calculate a correction bolus. (Intervention and control period)
5. Before driving to clinic for study visits. (Intervention and control period)
6. On arrival to clinic for study visits. (Intervention and control period)
7. Before and after exercise if they choose to exercise during the study period. (Intervention and control period)
8. On discharge from clinic for study visits. (Intervention period)

7-Day Control Period

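### The main paired Wilcoxon test ignores period although treatment order is randomized; the period-adjusted analysis should be the main one

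*Protocol*

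**What the plan says.** Study Type describes the design: "This is a multi-center, randomized, two treatment, crossover non-inferiority trial". Under Screening (Visit 1) the protocol states "The treatment order will be randomized" and that the two periods "will be a minimum of 7 days and a maximum of 8 weeks apart", counted from first day to first day. Neither section gives an allocation ratio or blocking. Participant Recruiting sets a goal of 30, "with up to 6 replacements as needed to collect data from 28 participants".

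For the primary endpoint, Statistical methods says "As our main approach, we will perform a two-sided Wilcoxon test for the paired differences". It then concedes the limitation: "However, it cannot accommodate missing data or estimate crossover effects, and while we do not anticipate that these will affect our study outcomes". For that reason, "we plan to conduct a supplemental analysis using a linear regression model with bootstrapped standard errors", with treatment, sequence and period terms. The sequence and period coefficients, "mean differences for sequence or period, are both expected to equal zero". A large or significant one is read as carryover. Nothing says that the adjusted result replaces the Wilcoxon result if the two differ.

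**The concern.** In a two-period crossover, each person's MPC-minus-control difference contains the period effect: subtracted for those who take MPC first, added for those who take it second. The main test pools these differences without regard to order. With equal sequences the period effect cancels in the mean but stays in the spread, so the test loses power. With unequal sequences part of it also stays in the mean, and a non-inferiority verdict read against a margin of a few points moves with it.

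A period effect is possible here. The two weeks can start as much as 8 weeks apart. The carbohydrate instruction card for exercise is handed out in both periods, so it is new only in the first. Equal sequences among those analysed are not assured, because the protocol states no blocking and allows withdrawals and replacements.

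**Working it through.** **Inputs.** From Power Analysis: N = 28, SD of the within-person difference 17 points, expected advantage 3.7 points, margin 6 points, one-sided 0.025, paired t test. Study Hypothesis gives a margin of 7; 6 is used here because the power statement uses it. The period effect π (second period minus first) has no figure in the protocol, so 0, 3, 5 and 8 points are assumed. The Wilcoxon test is taken as shifted by the margin, which the protocol does not state. Both the margin conflict and the missing shift are separate matters.

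**The plan's own figure.** Distance to the margin is 6 + 3.7 = 9.7. The standard error is 17/√28 = 3.21 and the noncentrality 9.7/3.21 = 3.02 on 27 df. Power is 82.9%, which agrees with the stated 80% or more. The smallest N reaching 80% is 27 (81.4%), so there is little slack.

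**Algebra.** Let τ be the treatment effect.

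- MPC first: expected difference τ − π. MPC second: τ + π.
- Shift of the pooled mean, given the split: π × (n MPC second − n MPC first)/N.
- SD of the pooled differences: √(17² + π² × [1 − ((n second − n first)/N)²]).

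At 14/14 the shift is zero and the SD is √(289 + 9) = 17.26 at π = 3, √(289 + 25) = 17.72 at π = 5, and √(289 + 64) = 18.79 at π = 8. At 16/12 the shift is 3 × 4/28 = 0.43 or 5 × 4/28 = 0.71 points. At 18/10 and π = 5 it is 5 × 8/28 = 1.43 points.

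**Simulated signed-rank test at the margin** (20,000 normal trials per setting, one-sided 0.025):

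| MPC first / second | π | Power | One-sided error |
|---|---|---|---|
| 14/14 | 0 | 80.7% | 2.3% |
| 14/14 | 3 | 80.1% | 2.3% |
| 14/14 | 5 | 78.2% | 2.1% |
| 14/14 | 8 | 73.8% | 1.4% |
| 16/12 | 3 | 76.4% | 1.4% |
| 16/12 | 5 | 71.6% | 1.3% |
| 12/16 | 3 | 83.3% | 3.2% |
| 12/16 | 5 | 83.8% | 3.3% |
| 18/10 | 5 | 64.4% | 0.7% |
| 10/18 | 5 | 88.8% | 5.0% |

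**Averaged over the split.** If order is assigned 1:1 independently, the differences at the margin are a symmetric mixture around it. The signed-rank error is then 2.3%, 2.4% and 2.5% at π = 3, 5 and 8 (40,000 trials).

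**Period-adjusted t.** Half the difference between sequences in mean period difference (second minus first) estimates τ free of π. Its standard error is (17/2) × √(1/n₁ + 1/n₂) on 26 df: 3.21 at 14/14, 3.25 at 16/12 and 3.35 at 18/10. Power is 82.8%, 82.0% and 79.5%, whatever π is. Simulated error lay between 2.3% and 2.7% in every setting.

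**How likely is imbalance?** Under simple 1:1 randomization of 28 (an assumption), the sequences differ by 4 or more with probability 0.57 and by 8 or more with probability 0.18.

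**The case against.** The protocol discloses the limitation and pre-specifies the adjusted model in response. With complete pairs, that model's treatment coefficient is the period-adjusted estimate above, so readers will see it. This stands, and it makes the change small. It does not settle the point, because the unadjusted test remains the main one and no rule covers disagreement.

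A reader might infer that the plan's false-claim rate is wrong. The documents do not support that. The inflation exists only conditional on an unequal realized split, in the direction that favours MPC; over 1:1 randomization the shift averages to zero and the error is held. The roughly 5% error needs an 18/10 split and a 5-point effect together, which is a stress case. Blocking, and the handling of replacements, may be set in a randomization plan that is not shown.

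A reader might also cite the Intervention Period's clinic training and meal-bolus advice as a source of a period effect. They belong to that arm in either position. Within its week they are part of treatment, and if they persist into Control they are carryover, which period adjustment does not remove.

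The sizes are assumed. Five points exceeds the whole expected advantage of 3.7. At 3 points and equal sequences the loss is under 1 point of power, and at 16/12 the shift is 0.43 points against a margin of 6 or 7. The contrast of 78% with 83% is also not all due to period: about 2 points is rank versus t, since signed-rank power is already about 81% with no period effect.

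**Conclusion.** The point holds as a matter of analysis choice and is worth correcting, though its expected size is modest. The main test leaves out a factor that the design controls, and the supplemental analysis that includes it has no stated standing. If there is a period effect, the cost is lost power on average. Given an unequal realized split there is also a shift of π times the imbalance over N: 0.7 points at 16/12 with a 5-point effect, where power is about 72% in one direction and one-sided error about 3.3% in the other. With small period effects and near-equal sequences the loss is slight. The figures assume normal differences with SD 17, a 6-point margin, a margin-shifted test and the period effects shown, none of which effects the protocol estimates.

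**What to change.** Make the main analysis period-adjusted. Compare within-person period differences between the two sequences, using either the two-sample t form on n − 2 df or the rank-sum form with its Hodges-Lehmann interval. Halve the contrast so that it is on the treatment scale, and read its confidence limit against the non-inferiority margin. State that this result governs, and keep the unadjusted paired Wilcoxon test as a sensitivity analysis.

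The change is to wording only, since sequence and period are already in the planned model. It costs one degree of freedom. If there is in truth no period effect, the t form has 82.8% power at 14/14, 82.0% at 16/12 and 79.5% at 18/10, against 82.9% for the paired t test: a loss of 0.1, 0.9 and 3.4 points, so roughly 0 to 4.

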Missing data: Our primary approach will include all available data as an intention-to-treat analysis, regardless of whether study subjects completed both arms. An observation will be included if at least 24 hours of data are available. However, we expect very low levels of missingness; in our previous four-arm crossover study, only one subject withdrew before completing at least two arms. Dropped CGM values will be interpolated over short time periods, using capillary values for calibration when available. In the event of $\geq 10\%$ missingness in either subject data or CGM values, we will analyze outcomes under multiple imputation to compensate for potential bias.

Additional considerations for selected secondary endpoints: The coefficient of variation of glucose is non-normal without an obvious probability distribution, so that bootstrapping will be

our primary approach for this endpoint. Data for percent of time with sensed glucose <54 mg/dl may be sparse; if so, we will present counts of events where glucose went below this level, counting as separate events when the time between them is ≥ 30 minutes.

Confidentiality and Protection of Human Participants

RISKS and BENEFITS

Risks: Given pumps and sensors used within automated glucose control systems are imperfect, there is a risk for hyperglycemia and hypoglycemia, which is mitigated by use of CGM alarms, protocols for managing hypoglycemia and hyperglycemia, and remote monitoring of the first 5 participants. A study investigator will be on call at all times.

Rarely, there can be allergic responses to insulin, such as skin redness, hives, itching of the skin, swelling of the mouth, or breathing difficulties. These reactions are considered very unlikely.

The following events have been identified as possible anticipated device-related adverse events of Dexcom G6 sensor insertion and wear:

- Excessive pain or discomfort from either system deployment or during wear period (8 or greater on a 10-point Likert scale)
- Excessive bleeding, defined as requires removal of the device to stop bleeding
- Hematoma, defined as induration at the sensor insertion location (ecchymosis is a known consequence of needle skin puncture or pressure from sensor pod and will not be captured as an AE)
- Edema from sensor and/or adhesive tape that is significant and non-resolving within 48 hours of sensor pod removal

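### The regression offered to handle missing data has no random subject effect, so its treatment estimate is biased when outcome-related dropout differs between the two sequences

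*Protocol*

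**What the plan says.** All of this stands in the protocol under Statistical methods.

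- The main approach is a paired Wilcoxon test, of which the protocol says "it cannot accommodate missing data or estimate crossover effects".
- For that reason it adds a second analysis: "we plan to conduct a supplemental analysis using a linear regression model with bootstrapped standard errors, which do not require distributional assumptions". The printed model is "Y_{ij} = \beta_0 + \beta_1 Trt_j + \beta_2 Seq_i + \beta_3 Period_j", with fixed terms only.
- Correlation within a person is handled in the bootstrap: "we will use study subjects as the sampling unit to account for correlation between their repeated observations".
- The Missing data paragraph retains one-period participants: "Our primary approach will include all available data as an intention-to-treat analysis, regardless of whether study subjects completed both arms". The minimum for a period is low: "An observation will be included if at least 24 hours of data are available".
- The fallback has a threshold: "In the event of $\geq 10\%$ missingness in either subject data or CGM values, we will analyze outcomes under multiple imputation".

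The regression is the only written analysis, below that threshold, that can use a participant with one period.

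**The concern.** A crossover analysis that keeps one-period participants should use the fact that a person's period 1 value predicts the missing period 2 value. The printed model cannot do so. A leaver's period 1 value stays in its own cell mean, while the matching period 2 mean is taken over those who stayed. If the leavers in one sequence had unusually low time in range, that period 2 mean is too high and the treatment coefficient moves.

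The direction depends on which period the leavers had first. Low-value leavers after Intervention push the estimate against the new system. Low-value leavers after Control push it in the new system's favour, the unsafe direction for a non-inferiority claim. Resampling whole subjects gives a suitable standard error but leaves the point estimate where it is. So the analysis added to cope with missing data copes, in general, only when the data are missing completely at random or the dropout is alike in both sequences.

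**Working it through.** **Inputs.** From Power Analysis: SDs of about 16 to 19 for the two conditions, SD of the within-subject difference 17, expected advantage 3.7, margin 6, one-sided 0.025, 28 subjects. From Participant Recruiting: 30 enrolled to obtain data from 28. The protocol gives no dropout rate and no dropout mechanism, so both are assumptions below.

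**The plan's own figure.** A one-sided paired t test with n = 28, SD 17 and distance 6 + 3.7 = 9.7 has power 82.9% (noncentral t), in line with the stated minimum of 80%. The standard error is 17/√28 = 3.2 (17/√30 = 3.1).

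**Implied correlation.** (16² + 19² − 17²)/(2 × 16 × 19) = 328/608 = 0.54.

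**What the coefficient estimates.** Four coefficients fit four cells exactly. Solving for the treatment term:

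β1 = ½[(Intervention mean, period 1 − Control mean, period 2) in the Intervention-first sequence + (Intervention mean, period 2 − Control mean, period 1) in the Control-first sequence].

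With complete pairs this equals the within-subject estimate. If k of the 15 people in one sequence leave after period 1, the period 2 mean of the stayers is expected to be too high by 0.54 × SD₂ × s. Here SD₂ is the SD in the missed condition and s is the amount, in SD units, by which the stayers' period 1 mean exceeds that of all 15. Hence |bias| = ½ × 0.54 × SD₂ × s.

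**Upper end: exactly the lowest period 1 values leave, all in one sequence.** The expected two lowest of 15 standard normal values are −1.736 and −1.248.

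| Leavers of 30 | s | Bias, SD₂ = 16 | Bias, SD₂ = 19 |
|---|---|---|---|
| 1 | 1.736/14 = 0.124 | 0.53 | 0.63 |
| 2 | (1.736 + 1.248)/13 = 0.230 | 0.99 | 1.18 |

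Simulation agrees. With 30 participants, both SDs 17.5, difference SD 17 and 2,500 runs, two leavers gave −1.10 (after Intervention) and +0.99 (after Control).

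**Moderate selection, still all in one sequence.** Suppose the chance weight of leaving doubles or triples per SD of lower time in range. Simulating s and applying the same formula gives 0.19 to 0.34 points for one leaver and 0.39 to 0.68 for two, so roughly 0.25 to 0.6 overall.

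**Dropout alike in both sequences.** With one lowest-value leaver per sequence, the two shifts have opposite signs: 0.63 − 0.53 = 0.10 with SDs 19 and 16, and zero with equal SDs. In simulation with equal SDs and the lowest values leaving equally from both sequences, the bias was at most 0.06. The shift goes into the period coefficient instead.

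**Dropout unrelated to outcome.** The simulated bias was between −0.05 and +0.07, which is simulation noise.

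**Alternatives, two lowest-value leavers in one sequence.**

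- Random subject intercept: −0.03 and −0.08 with equal SDs, and at most 0.26 in absolute value with SDs 16 and 19.
- Unstructured covariance by likelihood: at most 0.06 with SDs 16 and 19.
- Fixed subject effect: +0.92 and −1.03, so the bias keeps its size and changes sign.

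**Imputation threshold.** One or two of 30 is 3.3% or 6.7%, and three of 36 is 8.3%. All fall below 10%.

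**The case against.** The strongest reply is that the problem needs several conditions at once. Dropout must depend on the period 1 result, must differ between sequences, must leave under 24 hours of period 2 data, and must stay below the imputation threshold. The protocol expects very low missingness, citing one withdrawal before two arms in the earlier four-arm crossover. Under Return to the Outpatient Clinic, a visit stopped early may be repeated. The model-fit paragraph allows alternative specifications. All of this stands and limits the size of the point. It does not remove it: a single leaver cannot balance across sequences, two balance only by chance, and the model-fit paragraph concerns fit and influential points and does not commit to a subject effect.

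Three stronger readings are tempting and not supported.

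- **That any outcome-related dropout biases the estimate.** It does not; dropout alike in both sequences nearly cancels.
- **That the trial loses power or exceeds its type I error.** The protocol names the Wilcoxon test as the main approach and calls the regression supplemental. It attaches no rule for declaring non-inferiority to the regression's confidence limit. The words on a primary approach in the Missing data paragraph sit awkwardly with this, but they do not create such a rule.
- **That enrolling 30 for 28 means two one-period participants.** The protocol does not say that those lost would supply period 1 data or share a sequence.

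**Conclusion.** The point holds as a modest one. The regression is offered for missing data but uses one-period participants in a way that is biased when dropout is both outcome-related and unequal between sequences. With one or two leavers of 30 confined to one sequence, the bias is about 0.25 to 0.6 points under moderate selection (0.6/3.2, so up to about 0.2 of a standard error). It is at most about 0.5 to 1.2 points if exactly the lowest values leave (1.2/3.2, under 0.4 of a standard error). The sign depends on which period the leavers had first.

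These figures rest on the plan's SDs, normally distributed values, 15 people per sequence and assumed selection strengths. With complete pairs, or dropout unrelated to outcome, there is no bias. The paired Wilcoxon test is outside this point. A change is worthwhile because it is cheap, not because the trial's main conclusion is at risk.

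**What to change.** Under Statistical methods, replace the regression by a linear mixed model fitted by REML, with the same treatment, sequence and period terms and an unstructured 2x2 within-subject covariance. Name a random subject intercept as the fallback if that model does not converge, and do not use a fixed subject effect. Keep the subject-level bootstrap for the confidence interval. In the Missing data paragraph, state that this model is the all-available-data analysis whatever the share missing, so that correction does not wait for the 10% trigger.

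The cost is a few lines of text and a standard procedure, with no new data, participants or visits. With complete pairs the treatment estimate is unchanged. The small downside is a working covariance assumption, whose effect on inference the bootstrap limits. Validity still requires data missing at random.
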